12.1.9 Secondary Effectiveness Analysis

Superiority will be tested for the continuous effectiveness endpoints (e.g. Δ CAL, LBG, %BF, PD) using an ANCOVA model with the same baseline covariates as specified above and in addition, the corresponding baseline value for each endpoint. The ANCOVA model will include the same covariates as for the primary effectiveness endpoint. The two-sided 95% lower bound for the LSMEAN difference between each of the three GFeBGS treatment groups minus Active control will need to exceed 0 to achieve superiority.

Additional ANCOVA models will also evaluate any additional covariates found to be imbalanced ($p \leq 0.05$) at baseline.

Effectiveness outcomes will be displayed at every visit in order to characterize the time of onset and duration of effectiveness throughout the study. Results will be displayed for subjects who complete the study as planned as well as for those withdrawn early; the patterns of withdrawal will be displayed for each study treatment group to assess if reasons withdrawn were different in any respect.

Analyses will also be conducted for the other effectiveness endpoints inclusive of PDR, GR, WH, and BOP; the second composite endpoint (Δ CAL, %BF) will be analyzed in the same manner as for the first composite endpoint. In general, for continuous variables, the mean, median, standard deviation, minimum and maximum values will be displayed; for ordinal and categorical variables,

CONFIDENTIAL

frequencies and percentages will be displayed. When relevant, the mean changes from pre-operative baseline will be computed for all treatment groups at each visit through study exit; an unpaired t-test will be used to test for improvement between the treatment groups while a paired t-test will be used to test for improvement within the treatment groups. Superiority will be tested for continuous outcomes using an unpaired t-test by examining the two-sided 95% lower bound for the difference between GFeBGS minus Active control to test if the lower bound exceeds 0. The percents achieving predefined effectiveness milestones will be displayed at each post-baseline time through each stage; a two-sided Fisher Exact test will be used to test for superiority.

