12.0 STATISTICAL METHODS

Data will be summarized for each treatment group separately. The analyses will be performed by comparing the data for the active control group to each of the treatment groups.

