12.1.1 Hypothesis Testing

As this is a feasibility study, formal hypothesis tests for the purposes of regulatory approval or labeling claims will not be performed. Nonetheless, for internal purposes, statistical hypothesis tests may be performed as follows.

A two-sided superiority hypothesis test follows for the composite success percent endpoint:

$$\begin{aligned} H_0: p_G - p_C &= 0, \text{ versus} \\ H_a: p_G - p_C &\neq 0 \end{aligned}$$

where p_G and p_C are the respective percents of subjects achieving success as specified above for [REDACTED] GFeBGS and Active control treatment groups. This hypothesis testing format will be used for the other effectiveness endpoints measured as success outcomes.

The two-sided superiority hypothesis test is the following for the continuous and percent based measures relative to baseline:

$$\begin{aligned} H_0: \Delta_G - \Delta_C &= 0, \text{ versus} \\ H_a: \Delta_G - \Delta_C &\neq 0 \end{aligned}$$

where Δ_G and Δ_C are the respective mean changes in outcomes relative to baseline for [REDACTED] GFeBGS and Active control treatment groups. The same hypothesis testing format will be used for other continuous effectiveness endpoints.

For each primary and secondary effectiveness endpoint, an alpha level of 0.05 will be used.

CONFIDENTIAL

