12.1.2 Sample Size Determination

Since this is a feasibility study, the overall sample size was selected based on a combination of regulatory, logistical, and statistical considerations. While formal hypothesis testing for the primary effectiveness endpoint is not expected to be conclusive, the analysis of change in LBG is expected to provide more power as it is based on a continuous outcome. An assessment of the planned sample size based on this endpoint follows.

Sample size was determined based on a two-sided two sample unequal variance t-test with an overall 5% significance level for comparison of [REDACTED] GFeBGS versus Active control using the following assumptions:

- 1:1 randomization for GFeBGS and Active control (equal allocation of subjects to the control and each of the three treatment group separately, $n_1=n_2=n_3=n_4$ resulting in a 1:1:1:1 randomization allocation)
- Power = 80% for the secondary effectiveness endpoint of LBG
- $\delta = 1.70$ mm mean advantages in the change from baseline in LBG to be tested in favor of GFeBGS (3.00 mm) versus Active control (1.30 mm)
- Corresponding standard deviations (SDs) are projected to be 1.20 and 2.30 mm for the GFeBGS and Active control groups respectively
- 15% dropout rate by 6 month post-surgery.

With a minimum of 20 patients per treatment group, the power is at least 80% to detect a difference of 1.70 mm based on a two sample unequal variance t-test.

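### LBG is sized on unequal SDs (1.20 and 2.30 mm) but tested by an ANCOVA with no stated variance structure; run as one ordinary four-arm fit, its 95% intervals against control would cover about 90-91%

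*Protocol*

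**What the plan says.** Section 12.1.2 does not expect the primary test to be conclusive and looks to LBG for power. On the design test it states: "Sample size was determined based on a two-sided two sample unequal variance t-test with an overall 5% significance level". The sentence goes on to name a comparison of GFeBGS with the active control. On spread: "Corresponding standard deviations (SDs) are projected to be 1.20 and 2.30 mm for the GFeBGS and Active control groups respectively". On the result: "With a minimum of 20 patients per treatment group, the power is at least 80% to detect a difference of 1.70 mm".

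Section 12.1.9 names a different method. LBG and the other continuous endpoints are tested "using an ANCOVA model with the same baseline covariates as specified above and in addition, the corresponding baseline value for each endpoint". The decision rule is set on the lower limit of a two-sided 95% interval: the "LSMEAN difference between each of the three GFeBGS treatment groups minus Active control will need to exceed 0 to achieve superiority". Later the same section adds a second test: "Superiority will be tested for continuous outcomes using an unpaired t-test by examining the two-sided 95% lower bound for the difference". Neither rule says how variances are handled, and the section does not say whether the ANCOVA is one fit to all four arms or three separate fits.

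Section 12.0 bears on that last question: "The analyses will be performed by comparing the data for the active control group to each of the treatment groups".

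On status, section 12.1.1 says that "for internal purposes, statistical hypothesis tests may be performed as follows". Section 12.1.10 bases dose selection on the binary composite, not on LBG.

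**The concern.** The design calculation takes the control SD to be nearly twice the GFeBGS SD and uses a test that allows for this. The analysis section names a model whose default form does not. An ordinary ANCOVA on four arms estimates one residual variance. Three of the four arms are projected to have the low variance, so the estimate is pulled well below what a comparison with the high-variance control needs. Every dose-control interval is then too narrow, whether or not the product works.

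What is at stake is the LBG evidence carried into pivotal planning. It would look more precise than it is, and apparent power would exceed the 80% that 12.1.2 calculated.

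**Working it through.** **Inputs.** From 12.1.2: difference 1.70 mm (3.00 against 1.30), SD 1.20 mm (GFeBGS) and 2.30 mm (control), 20 evaluable per arm, two-sided 5%. Assumption: 1.20 mm applies to each of the three dose arms, since the protocol gives one SD for GFeBGS.

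**Step 1: reproduce the stated power (one dose against control, Welch).**
- SE = sqrt((1.20² + 2.30²)/20) = sqrt((1.44 + 5.29)/20) = 0.580 mm
- Satterthwaite df = (0.072 + 0.2645)² / ((0.072² + 0.2645²)/19) = 28.6
- Noncentrality = 1.70/0.580 = 2.93
- Power = 80.8% at 20 per arm; 19 per arm gives 78.6%

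The plan's figure is right, at two-sided 5% for a single dose-control comparison.

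**Step 2: the standard error in one ordinary four-arm fit.**
- Pooled variance = (3 × 1.44 + 5.29)/4 = 2.4025, so the pooled SD is 1.55 mm
- Model SE = sqrt(2.4025 × 2/20) = 0.490 mm
- Ratio to the true SE = 0.490/0.580 = 0.845, about 16% too small
- Normal approximation to coverage: 2Φ(1.96 × 0.845) − 1 = 90.2%

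**Step 3: the standard error in separate two-arm fits.** With equal arms the pooled variance is (1.44 + 5.29)/2 = 3.365, and sqrt(3.365 × 2/20) = 0.580 mm. The SE is correct; only the degrees of freedom are somewhat too generous.

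**Step 4: simulation.** 20,000 trials per case, 20 per arm, ANCOVA with age group, smoking and a baseline value, all assumed unrelated to outcome. The Welch row is unadjusted. The column for no true difference keeps the SDs unequal.

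| Analysis | Coverage, no difference | Lower bound above 0, no difference | Coverage, true 1.70 mm | Power at 1.70 mm |
|---|---|---|---|---|
| One four-arm fit, common variance | 90.3% | 4.8% | 90.3% | 88.3% |
| Separate two-arm fits | 94.8% | 2.7% | 94.5% | 77.7% |
| Welch t-test | 95.0% | 2.5% | 94.9% | 80.5% |
| Four-arm fit, HC3 errors | 95.3% | 2.4% | 95.2% | 78.4% |

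Independent repeats of the four-arm case under no difference gave coverage of 90.1% to 90.9% and false superiority of 4.4% to 4.9%. A fit with arm-specific variances and Satterthwaite df gave 95.3% and 2.3%. The mean 95% half-width is 0.99 mm in the four-arm fit and 1.18 mm with Welch.

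**Step 5: sensitivity.**
- With control SD 1.6 mm, the four-arm fit covers 93.1% with 3.5% false superiority.
- With equal SDs there is no problem.
- With 18 control and 22 per dose, the four-arm fit gives 88.5% and 5.6%; two-arm fits give 93.5% and 3.0%.
- With 22 control and 18 per dose, the four-arm fit gives 92.3% and 3.8%; two-arm fits give 95.8% and 2.1%.

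**The case against.** The strongest reply is that the protocol nowhere specifies a common variance. Number of fits, variance structure and degrees of freedom are commonly left to the statistical analysis plan. The text also gives support to separate fits: section 12.0 compares control with each group, 12.1.1 writes two-group hypotheses, and 12.1.2 speaks of each dose group separately. On that reading coverage is about 94.5% or better with equal arms, and 1:1:1:1 blocked randomization gives no reason to expect a marked shortfall in control. This stands, and it makes the point conditional. A reader might infer that the protocol commits itself to invalid intervals; the documents do not support that. What remains is that the default form of the named model fails under the protocol's own projected SDs, and nothing in 12.1.9 prevents that form from being used.

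It is also fair to say that sizing on a t-test and analysing by ANCOVA is ordinary practice, and that 12.1.9 plans an unpaired t-test as well. The difference in method is not itself the fault; the variance assumption is. Which of the two tests ranks first can be left to the analysis plan.

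A reader might take the word *overall* in 12.1.2 as a familywise claim over three doses, under which power would be about 65% (Bonferroni, 0.0167 each). The documents do not support that. The sentence describes one comparison of GFeBGS with control, the stated power is correct for it, 12.1.9 sets an unadjusted bound for each dose, and no section claims familywise control.

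**Conclusion.** The concern holds in conditional form and is minor. If the 12.1.9 ANCOVA is run as one common-variance four-arm fit, control SD is 2.30 mm, every dose SD is 1.20 mm and arms are equal at 20, then nominal 95% intervals against control cover about 90-91%. False superiority is about 4.4-4.9% per dose instead of 2.5%. The under-coverage is the same at a true 1.70 mm, so it does not depend on the product being ineffective. The false-superiority rate does need equal means with the SD gap intact. The problem shrinks as the SDs converge and nearly vanishes with two-arm fits and equal arms.

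A reader might infer that dose selection is compromised. It is not: 12.1.10 uses the composite, LBG is secondary, and the tests are optional, internal and not for labeling. The wording of the 5% level in 12.1.2 is an editorial matter only; the sample size needs no change.

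**What to change.** In 12.1.9, state that the ANCOVA for continuous endpoints is fitted with arm-specific residual variances and Satterthwaite degrees of freedom, or with HC3 standard errors. State that the unpaired t-test is the unequal-variance form, to match 12.1.2. This works whether one four-arm fit or separate fits were intended.

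In 12.1.2, replace the description of the level as overall by: two-sided 5% for each dose-control comparison.

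The cost is one model option and a few words, with no change to data, sample size or conduct. Apparent power at 1.70 mm falls from about 88% under the four-arm fit to about 78-81% (HC3 78.4%, Welch 80.5%), which is what 12.1.2 planned for. These powers assume covariates unrelated to outcome, so any gain from adjustment would come on top.

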12.1.8 Primary Effectiveness Analysis

Comparisons will be made between the control group and each of the treatment groups using 2x2 tables. Superiority for the composite endpoint will be tested using a logistic regression model to include age (< 50 versus \geq 50 years) and smoking status (never or not within the last 6 months vs. any within the last 6 months) at the time of randomization as the baseline covariates. The two-sided 95% lower bound for the LSMEAN difference for each of the three GFeBGS treatment groups minus the Active control will need to exceed 0% to achieve superiority. An unadjusted logistic regression model for the primary composite endpoint will also be performed.

Superiority will also be tested using an exact two-sided 95% lower confidence bound for the difference in success percents. The two-sided 95% lower bound for each of the three GFeBGS treatment groups minus Active control difference must be \geq 0% to achieve superiority.

Additional logistic regression models will also evaluate any additional covariates found to be imbalanced ($p \leq 0.05$) at baseline.

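### Fisher's exact test on the secondary milestone percents uses at most about half of the permitted 5% at 20 per arm; an exact unconditional test would recover power at no cost (low severity)

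*Protocol*

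**What the plan says.** Section 12.1.1 (Hypothesis Testing) fixes the level: "For each primary and secondary effectiveness endpoint, an alpha level of 0.05 will be used". It makes the tests two-sided. It also says that formal tests for approval or labeling will not be performed, and that tests may be run for internal purposes.

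Section 12.1.9 (Secondary Effectiveness Analysis) deals with the milestone outcomes in one sentence. Its first half reads "The percents achieving predefined effectiveness milestones will be displayed at each post-baseline time through each stage". Its second half names the test: "a two-sided Fisher Exact test will be used to test for superiority".

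The two composite endpoints are handled differently. For the primary composite, section 12.1.8 states "Superiority for the composite endpoint will be tested using a logistic regression model to include age" and smoking status, adds an unadjusted logistic model, and then adds a further criterion: "Superiority will also be tested using an exact two-sided 95% lower confidence bound for the difference in success percents". Section 12.1.9 says that the second composite "will be analyzed in the same manner as for the first composite endpoint".

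On size, section 12.1.2 says "With a minimum of 20 patients per treatment group, the power is at least 80% to detect a difference of 1.70 mm". That statement concerns linear bone growth, a continuous outcome. No success rate or power is given for any binary outcome.

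**The concern.** Fisher's test conditions on the total number of successes in the two arms. With about 20 subjects per arm, few tables are possible at each total, so the attainable p-values are widely spaced. The largest one at or below 0.05 is often well below it, and the unused part of the 5% is lost as power. In a trial this small, a real difference in a milestone percent can then go undetected because of the test and not because of the data. Exact unconditional tests hold the same 5% ceiling with less waste. The protocol itself names Fisher's test for this comparison, so the choice can be reviewed without the statistical analysis plan.

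**Working it through.** **Inputs from the protocol.** Two-sided level 0.05 (12.1.1); minimum 20 per group (12.1.2); 94 randomized 1:1:1:1 (5.1, 12.1.2), so 94/4 = 23.5 per arm before dropout. The calculation is done at 20 and at 23 per arm to cover the range from the planned dropout to almost none.

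**Assumed inputs.** Success rates per arm. The protocol gives none, so a range is shown.

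**The plan's own figure first.** For linear bone growth with 20 per arm, a difference of 1.70 mm and SDs of 1.20 and 2.30 mm:
- Standard error = √((1.20² + 2.30²)/20) = √(6.73/20) = 0.580.
- Noncentrality = 1.70/0.580 = 2.93; Satterthwaite df = 28.6.
- Two-sided 5% power = 80.8%.

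The stated 80% at 20 per arm is reproduced. It does not bear on binary outcomes, for which there is no stated figure to check.

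**Method for binary outcomes.** List every pair (a, b) with a and b from 0 to n, giving 21 × 21 tables at n = 20. For a rejection region R:

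Power(p₁, p₂) = Σ over (a, b) in R of Bin(a; n, p₁) × Bin(b; n, p₂)

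True size is the maximum of this over a common rate p₁ = p₂, scanned from 0.001 to 0.999. Fisher's region is all tables with two-sided p ≤ 0.05. Boschloo's region is all tables with Fisher p ≤ c, where c is the largest attained value that keeps the maximum size at or below 5%.

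**True size.**

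| n per arm | Fisher, maximum | Boschloo cut-off c | Boschloo, maximum |
|---|---|---|---|
| 20 | 2.53% | 0.0915 | 4.64% |
| 23 | 2.60% | 0.0746 | 4.75% |

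At n = 20 Fisher's size is 2.0% to 2.5% for common rates from 15% to 50%, 1.2% at 10% and 0.2% at 5%. Because c is above 0.05, Boschloo's region contains Fisher's, so Boschloo is never less powerful.

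**Power at 20 per arm (%).**

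| Assumed rates | Fisher | Boschloo | Gain (points) |
|---|---|---|---|
| 30 v 60 | 34.7 | 44.7 | 9.9 |
| 50 v 80 | 40.9 | 49.2 | 8.3 |
| 60 v 90 | 49.2 | 60.9 | 11.7 |
| 50 v 85 | 57.3 | 66.1 | 8.8 |
| 30 v 70 | 59.9 | 70.5 | 10.6 |
| 20 v 60 | 65.0 | 72.8 | 7.8 |
| 10 v 50 | 74.2 | 82.2 | 7.9 |
| 55 v 95 | 81.8 | 88.8 | 6.9 |
| 30 v 80 | 84.6 | 90.1 | 5.5 |
| 10 v 60 | 90.8 | 94.1 | 3.2 |
| 20 v 80 | 96.1 | 98.1 | 2.0 |
| 20 v 30 | 6.2 | 10.5 | 4.3 |

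(Gains come from unrounded powers.) Where Fisher has about 35% to 75% power the gain is 7.8 to 11.7 points. It is 6.9 points at 55 v 95, and 2.0 to 5.5 points at the very high or very low power pairs.

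**Power at 23 per arm.** At pairs of the same moderate kind the gain is about 5 to 10 points: 50 v 80, 46.2% to 56.1%; 30 v 70, 71.3% to 78.6%; 10 v 50, 81.1% to 85.8%.

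**Examples at 20 per arm.** Results of 15/20 v 8/20, 14/20 v 7/20 and 18/20 v 12/20 have Fisher p = 0.054, 0.056 and 0.065. Fisher's test does not reject them; Boschloo's does, with its error still at or below 5%.

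**The case against.** **Nothing stated is wrong.** A reader might infer that the stated 5% is an error because the true size is about 2.5%. The documents do not support that. The 0.05 is a ceiling and Fisher's test respects it. The choice is between two valid tests. This stands in full.

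**Fisher does not test the primary composite.** A reader might also infer that the main binary comparison runs at 2.5%. It does not. Both composites are tested mainly by logistic regression (12.1.8, 12.1.9), and dose selection uses logistic contrasts (12.1.10). The power loss shown above does not carry over to either.

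**The exact bound in 12.1.8.** It is tempting to extend the point to this bound, since the protocol does not say how it is constructed. That detail is commonly left to the statistical analysis plan, so its absence is no finding. Nor would a bound ordered on the raw difference be generally worse than Fisher's test: at 30% v 70% its power is 70.3%, against 59.9% for Fisher and 70.5% for Boschloo.

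**Little depends on it.** Section 12.1.1 describes the tests as internal, section 12.1.2 does not expect the primary binary test to be conclusive, and the Study Summary lets the sponsor take any of the three doses forward. This stands and keeps the severity low.

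**Conservatism might offset three unadjusted dose comparisons.** It does so in part, but not by design: Fisher's size moves between 0.2% and 2.5% with the unknown success rate, so it cannot serve as planned multiplicity control.

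**Conclusion.** The point holds as an optional efficiency gain of low severity, confined to the two-arm comparisons of secondary milestone percents in 12.1.9. At 20 per arm Fisher's test leaves about half of the permitted 5% unused. Boschloo's test stays within 5% and recovers about 7 to 12 points of power at moderate effects and about 2 to 6 points elsewhere. At 23 per arm the moderate-effect gain is about 5 to 10 points.

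The sizes and the dominance of Boschloo over Fisher follow from n and the 0.05 level alone. The power gains also rest on assumed success rates. The conclusion does not extend to the composites' main tests, to dose selection, or to the correctness of any stated figure.

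**What to change.** In section 12.1.9, for two-arm comparisons of milestone percents, replace Fisher's test with Boschloo's exact unconditional test at two-sided 0.05. A score-ordered exact unconditional test would serve nearly as well, although the guarantee of rejecting whenever Fisher's test does belongs to Boschloo's. This point calls for no change to section 12.1.8 or 12.1.10.

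The cost is one sentence and standard software. It needs no extra subjects or data, and the type I error of each comparison stays at or below 5%. The change should be made before unblinding, so that the test is not chosen with the results in view.

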12.1.10 Dose Selection

Dose selection for future study will be based on an analysis of the primary composite endpoint. Five different dose response patterns will be examined and modeled statistically, with the dose selected based on the best model fit. Specifically, we will perform a logistic regression of the primary composite endpoint and apply linear contrasts to the model according to the following five dose response patterns for success:

1. An increase in a linear manner from the Treatment I to Treatment IV groups
2. A plateau in the Treatment II group, with similar performance in groups II through IV
3. A plateau in the Treatment III group, with similar performance in group IV
4. An apex in the Treatment III group; best performance in group III, lower performance in the other groups
5. An apex in the Treatment IV group; best performance in group IV, lower performance in the other groups

For each contrast, the Wald test statistic will be computed and the pattern that corresponds to the largest value of the Wald statistic will be considered the best fit and guide the selection of the optimal dose.

For patterns where there is insufficient data to distinguish between effective doses, patterns 2 and 3 for example, the 0.3% rh-bFGF dose may be selected based on prior data and pre-clinical testing.

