The secondary endpoints will include the mean Δ CAL from baseline at three and six months and the mean Δ CAL between study treatments at three and six months post-implantation; the LBG at six months; percent bone fill (%BF) in a vertical and horizontal direction compared to baseline and six months post-implantation, a composite endpoint combining Δ CAL and %BF; Probing Depth Reduction (PDR) from baseline at three and six months post-implantation, Change in Gingival Recession (Δ GR) from baseline at three and six months post-implantation; Wound-Healing (WH) scale and gingival wound evaluation during the first four weeks, and bleeding on probing (BOP) at three months.

Dose Selection Overview:

The goal of the feasibility study is to identify either the 0.1%, 0.3% or 0.4% active dose to be compared vs. the β -TCP control in a pivotal study, based on the observed safety and effectiveness together with past study results. No formal interim analyses are planned.

This study will not be used for labeling purposes, but will be used to plan the subsequent pivotal study. The Sponsor retains the right to pick any of the three active doses moving forward to the pivotal study.

Statistical Considerations:

The primary effectiveness endpoint is a composite endpoint that considers radiographic and clinical measurements at six months post-implantation: the amount of linear bone growth (LBG), which is assessed with the use of radiographs, and the change from baseline of clinical attachment level (Δ CAL), which is calculated from clinical assessments. To be a success, Δ CAL ($CAL_{6\text{ mo}} - CAL_{\text{Baseline}}$) must be at least -1.5 mm and a minimum measurement of 1 mm is required for linear bone growth (LBG) measured from baseline; both must be met at 6 months to define a primary effectiveness success for the tooth (Lynch S, Lavin P *et al. J Periodontal* 2006;77:1314). The number of teeth that meet the success criteria for the primary endpoint will be compared between the study treatments. The components of the primary effectiveness outcome, including LBG in particular, are also of interest.

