5.0 STUDY DESIGN AND DESCRIPTION

5.1 Study Design

This will be a prospective, randomized, double-blinded, controlled, multi-center, dose-verification clinical study in subjects who require surgical intervention to treat a qualifying periodontal defect. A total of 94 subjects will be randomized to obtain at least 80 evaluable subjects in anticipation of a 15% dropout rate. This study will be conducted in six sites in the United States.

The duration of the study for each subject will be six months following implantation of the study device.

Subjects will participate in a Screening Period lasting up to 2.5 months. Subjects must have been diagnosed to have at least one periodontally related osseous defect to be treated by periodontal reconstructive surgery. Subjects must be systemically healthy and not have any sites suffering from localized juvenile periodontitis. Subjects must not partake in the daily use of smokeless chewing tobacco, pipe or cigar smoking, or smoke more than 10 cigarettes a day or the equivalent.

After a successful screening, eligible subjects will be randomized using variable block sizes for the four treatment groups. The study will be stratified to control for potential differences in healing rates and responses in the treatment based on smoking habits (between non-smokers and moderate smokers).

The treatment groups are:

Treatment I: β -TCP alone (active control)

Treatment II: [REDACTED] GFeBGS: consisting of β -TCP and 0.1% rh-bFGF

Treatment III: [REDACTED] GFeBGS: consisting of β -TCP and 0.3% rh-bFGF

Treatment IV: [REDACTED] GFeBGS: consisting of β -TCP and 0.4% rh-bFGF

Subjects will be evaluated at 2 and 4 weeks and 3 and 6 months following surgery (see Figure 5).

Figure 5 Schematic of Study Visits and Windows

| | Screening period | Pre-treatment procedures | | | Treatment/ Post-treatment follow-up period | | | | |
|-----------|------------------|---------------------------------------|---------------|----------|--|--------------|--------------|--------------|---------------------------------|
| Visit # | Visit 1 | Visit 2 | Visit 3 | Visit 4 | Visit 5 | Visit 6 | Visit 7 | Visit 8 | Visit 9 |
| Procedure | Screening | Pre-treatment | Pre-treatment | Baseline | Surgery | Wk 2 | Wk 4 (1 Mo) | 3 Mo (12 Wk) | 6 Mo/ Early termination (24 Wk) |
| Schedule | <-3 Mo | -2 Mo (\geq 2Wks before Baseline)* | -2 Wks | | | | | | |
| Windows | | (-2 days)* | | Day 1 | \pm 3 days | \pm 3 days | \pm 7 days | \pm 7 days | |

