7.0 INVESTIGATIONAL DEVICE DESCRIPTION

7.1 Investigational Device

7.1.1 Manufacturing, Packaging, and Labeling

7.1.1.1 Description of Investigational Device

1. Components

The investigational device, [REDACTED] GFeBGS, is supplied in a kit which consists of three components and one accessory:

- 1 each sterile β -TCP in a portion cup
- 1 each vial that contains a sterile lyophilized cake with rh-bFGF.
- 1 each sterile HPC solution in a syringe
- 1 each 18G blunt needle

2. Product code: [REDACTED]

3. Generic name:

rh-bFGF: trafermin (genetic recombinant)
 β - TCP: β - tricalcium phosphate

4. Molecular formula:

rh-bFGF: $C_{764}H_{1201}N_{217}O_{219}S_6$ (Protein composed of 154 amino acids) or
 $C_{761}H_{1196}N_{216}O_{218}S_6$ (Protein composed of 153 amino acids)
 β - TCP: $Ca_3(PO_4)_2$

5. Molecular weight:

rh-bFGF: 17,122.67 (Protein composed of 154 amino acids) or
17,051.59 (Protein composed of 153 amino acids)
 β - TCP: 310.18

6. Content of active ingredients

- Treatment I: β -TCP with 0.5 mg trafermin-containing lyophilized rh-FGF (final conc. 0.1%)
- Treatment II: β -TCP with 1.5 mg trafermin-containing lyophilized rh-FGF (final conc. 0.3%)
- Treatment III: β -TCP with 2.0 mg trafermin-containing lyophilized rh-FGF (final conc. 0.4%)

CONFIDENTIAL

- Treatment IV: β -TCP with lyophilized vial (Active control)

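### The five dose-response patterns used to guide dose selection include no apex at 0.1%, although 0.1% is one of the three doses the study may identify

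*Protocol*

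**What the plan says.** The Study Summary gives the aim under Dose Selection Overview: "The goal of the feasibility study is to identify either the 0.1%, 0.3% or 0.4% active dose" to take into a pivotal study. It adds: "The Sponsor retains the right to pick any of the three active doses moving forward to the pivotal study".

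Section 12.1.10 bases selection on the primary composite endpoint: "Five different dose response patterns will be examined and modeled statistically, with the dose selected based on the best model fit". The five patterns, written in treatment numbers only, are a linear rise from I to IV, a plateau starting at II, a plateau starting at III, an apex at III and an apex at IV. Pattern 4, for example, reads: "An apex in the Treatment III group; best performance in group III, lower performance in the other groups". The contrast with the largest Wald statistic is taken as the best fit and guides the choice. The text does not say whether the statistic is signed or squared. Where the data cannot separate effective doses, the fallback is: "patterns 2 and 3 for example, the 0.3% rh-bFGF dose may be selected based on prior data and pre-clinical testing".

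In the Study Summary and Section 5.1, Treatment I is the control, II is the product "consisting of β -TCP and 0.1% rh-bFGF", III is 0.3% and IV is 0.4%. Section 7.1.1.1 numbers the arms differently: I is 0.1%, II is 0.3%, III is 0.4%, and the last line reads "Treatment IV: β -TCP with lyophilized vial (Active control").

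**The concern.** Three doses are candidates, but only two have a shape in which they are uniquely best. If success peaks at 0.1% and falls away above it, the analysis must report some other shape. The nearest is the plateau starting at Treatment II, which says the three doses perform alike and is one of the two patterns named for the possible 0.3% fallback. The same advantage at 0.3% or 0.4% has a pattern of its own.

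The primary objective is to obtain dosing data and guide the dose for a later study, so what this analysis is able to report matters. Two further points affect how it is run. An unsigned statistic lets a contrast win by pointing the wrong way, and patterns written in treatment numbers rely on a numbering that the protocol gives in two versions.

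**Working it through.** **The plan's own figure.** Section 12.1.10 gives no operating characteristics. The only power figure is in Section 12.1.2: at least 80% for linear bone growth with 20 per arm. SE = √[(1.20² + 2.30²)/20] = √0.3365 = 0.580; 1.70/0.580 = 2.93; with Satterthwaite df 28.6 and two-sided 5%, power is 0.808. It reproduces. Only n = 20 per arm is carried forward.

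**Which group is best in each pattern** (numbering of the Study Summary and Section 5.1):

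| Pattern | Top group(s) | Dose(s) |
|---|---|---|
| 1 linear | IV | 0.4% |
| 2 plateau from II | II, III, IV tied | all three |
| 3 plateau from III | III, IV tied | 0.3%, 0.4% |
| 4 apex III | III | 0.3% |
| 5 apex IV | IV | 0.4% |

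No row has 0.1% alone. Under Section 7.1.1.1, where 0.1% is Treatment I, there is no apex at 0.1% either. This part needs no assumption.

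**What the rule would report.** The protocol gives neither success rates nor contrast coefficients, so both are assumed. Order: control, 0.1%, 0.3%, 0.4%. Set A: linear (-3,-1,1,3), plateau II (-3,1,1,1), plateau III (-1,-1,1,1), apex III (-1,-1,3,-1), apex IV (-1,-1,-1,3). Set B: linear (-2,-1,1,2) and plateau III (-5,-1,3,3), others as in A. Added contrast: apex II (-1,3,-1,-1).

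Take true rates 50/80/50/50%. The log odds are 0, ln 4 = 1.386, 0, 0. The variances are 1/[n p(1-p)]: 1/(20 × 0.25) = 0.2 for the 50% arms and 1/(20 × 0.16) = 0.3125 for the 80% arm. With z = Σcᵢ logitᵢ / √(Σcᵢ² varᵢ), set A gives:

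| Contrast | Numerator | SE | z | z² |
|---|---|---|---|---|
| linear | -1.386 | √4.1125 = 2.028 | -0.68 | 0.47 |
| plateau II | 1.386 | √2.5125 = 1.585 | 0.87 | 0.76 |
| plateau III | -1.386 | √0.9125 = 0.955 | -1.45 | 2.11 |
| apex III | -1.386 | √2.5125 = 1.585 | -0.87 | 0.76 |
| apex IV | -1.386 | √2.5125 = 1.585 | -0.87 | 0.76 |
| apex II (added) | 4.159 | √3.4125 = 1.847 | 2.25 | 5.07 |

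Signed, plateau II is the only positive contrast of the five. Squared, plateau III leads because it points strongly the wrong way. The added contrast leads on either form.

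**Simulation** (100,000 trials per scenario, binomial, 20 per arm, 0.5 added to each cell, no covariates; ranges are over sets A and B):

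| True rates (%) | Statistic | Five patterns | With apex II added |
|---|---|---|---|
| 50/80/50/50 | signed | plateau II 88%, apex III 6%, apex IV 6% | apex II 88%, plateau II 9% |
| 50/80/50/50 | squared | plateau II 31-35% (set A: plateau III 40%) | apex II 64-69% |
| 40/70/50/50 | signed | plateau II 84% | apex II 62%, plateau II 28-29% |
| 40/70/60/60 | signed | apex II impossible | apex II about 26%, plateau II 57-58% |
| 40/70/60/60 | squared | apex II impossible | apex II about 23% |
| 50/50/80/50 | signed | apex III 78-82% | apex III 77-81% |
| 50/50/50/80 | signed | apex IV 71-74% | apex IV 70-73% |
| 40/70/70/70 | signed | plateau II 77% (A), 72% (B) | plateau II 72% (A), 67% (B) |

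In the first row, the observed 0.1% rate is strictly the highest of the four arms in 97% of the trials reported as plateau II.

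**The case against.** - **The candidate set may be deliberate.** The gel studies in Section 3.3 report significant bone-height gains at 0.2% and above and suggest no peak at the lowest dose. That is a plausible reason, but the protocol does not give it. Section 12.1.10 cites prior data only for the fallback, and Section 3.3 calls this the first study of the combined device.
- **Nothing is binding.** This stands. The fit guides selection, safety and past results also count, and the sponsor may take any active dose. A reader might infer that 0.1% is excluded; the documents do not support that.
- **The fallback is conditional.** This stands too. It applies when effective doses cannot be told apart, and then 0.3% may be chosen. A reader might infer that a plateau-II result switches selection to 0.3%; the wording does not say so. At 50/80/50/50%, 0.1% leads the next active arm by at least 20 points in 75% of plateau-II trials (signed), and the 2x2 tables of Section 12.1.8 would show it. Those tables are a partial safeguard only. They set each dose against control, and 0.1% beats control in 41% of trials (Fisher) or 46% (unadjusted Wald). Section 12.1.2 itself says "formal hypothesis testing for the primary effectiveness endpoint is not expected to be conclusive".
- **The sizes depend on the form of the statistic.** Correct. A claim that a peak at 0.1% is mostly reported as a plateau holds for the signed form only.
- **The numbering resolves itself.** Largely so. Under Section 7.1.1.1 the pattern-3 plateau would be 0.4% and control, so a 0.3% fallback would make no sense there. A reader might fear contrasts attached to the wrong arms; that is unlikely. The two lists still contradict each other.
- **A later analysis plan may give coefficients.** It may, but the protocol already fixes the list of five patterns.

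**Conclusion.** The point holds as a limit on what the analysis can report. With the five listed patterns the probability of naming 0.1% as uniquely best is zero whatever the data, while 0.3% and 0.4% each have an apex pattern. That follows from the text alone.

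The size rests on assumed rates and contrasts. With a clear peak at 0.1% (50/80/50/50%), the added contrast takes a correct report from 0 to 88% (signed) or 64-69% (squared). With a modest peak (40/70/60/60%) it reaches only about 26% or 23%. The sign of the Wald statistic matters more here than the choice between the two coefficient sets, so it has to be fixed together with the pattern list. The numbering conflict is editorial. The point is worth correcting before unblinding, but it does not invalidate the study, and no view is taken on which dose should be chosen.

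**What to change.** In Section 12.1.10:

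1. Add a sixth contrast with its apex at 0.1%, so that each selectable dose has one. If it is left out on purpose, give the reason.
2. State that the Wald statistic is signed and that the winning contrast must be positive; otherwise report that no pattern is supported.
3. Name the patterns by concentration instead of treatment number.

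Separately, reconcile the arm numbering in Section 7.1.1.1 with the Study Summary and Section 5.1.

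The cost is wording and programming, with no change to sample size or visits. Identification of a true plateau from 0.1% (40/70/70/70%) falls by about 4-5 points. With the signed statistic, identification of a true apex at 0.3% or 0.4% falls by at most about 1 point.
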